9.2 Statistical Hypotheses

This is a single arm study (i.e., no sham, placebo or alternative treatment included). The primary objective (clinical success rate) is a binary assessment of whether or not each patient achieved clinical success at 6 months post intervention.

The study is designed to test the null hypothesis (H_0) that the true proportion (PT) of patients that will manifest a positive treatment response, is no greater than 0.5 against the one-sided alternative hypothesis (H_A) that $PT \geq 0.75$.

The response rate will be summarized in terms of the observed proportion of patients manifesting a positive response and a two-sided exact 95% confidence interval (CI) per the Blyth-Still-Casella method (31). The treatment will be declared a success if the data support the conclusion that at least 75% of treated patients can be expected to show a positive response. The treatment will be considered unworthy of additional study without further

development if the data are consistent with the conclusion that no more than 50% of treated patients can be expected to show a positive response.

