9.4 Description of Statistical Methods

9.4.1 General Approach

This is a single arm study (i.e., no sham, placebo or alternative treatment included). The primary objective (clinical success rate) will be assessed as a binary outcome of whether or not each patient shows clinical success as defined above. The response rate will be summarized in terms of the observed proportion of patients manifesting a positive response and a two-sided exact 95% confidence interval (CI) per the Blyth-Still-Casella method. KOOS pain scores and pain VAS will be assessed as mean and standard deviation.

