9.5 Sample Size

The sample size is selected based on primary objective so that the study will have 80% power at the 5% significance level for testing the null hypothesis $H_0: PT \leq 0.5$ against the alternative hypothesis $H_A: PT \geq 0.75$, where PT is the true proportion of patients that will manifest a positive treatment response. As a result, the study should have 40 patients who completed the 6 months visit since this sample size will endow the test with 80.4% power at a realized significance level of 0.047 with 20% attrition, the study will need 50 subjects to reach the target sample size.

With 20% with 20% attrition, the study will need to enroll 50 patients. The PI and sub-investigators determined that increase in the sample size is necessary to evaluate the role of GAE as a disease-modifying treatment option for knee OA. Since this current study is the only active study in the U.S collecting samples for biomarker analysis and the need for a larger sample size to evaluate changes in biomarker levels, an increase in sample size is needed.

10 Source Documents and Access to Source Data/Documents

Source data is all information, original records of clinical findings, observations, or other activities in a clinical trial necessary for the reconstruction and evaluation of the trial. Source data are contained in source documents.

Examples of these original documents, and data records include: hospital records, clinical and office charts, laboratory notes, memoranda, subjects' diaries or evaluation checklists, pharmacy dispensing records, recorded data from automated instruments, copies or transcriptions certified after verification as being accurate and complete, microfiches, photographic negatives, microfilm or magnetic media, x-rays or other imaging studies, subject files, and records kept at the pharmacy, at the laboratories, and at medico-technical departments involved in the clinical trial. It is acceptable to use paper CRFs as source documents. Source CRFs can also be documented in the electronic medical record (EPIC).

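### The plan does not say whether the one-sided 5% test or the two-sided 95% interval decides the 50% rule; at n = 40 they disagree at 26 responders

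*Combined protocol and SAP*

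**What the plan says.** Section 9.2 states the null hypothesis that the true response proportion "is no greater than 0.5 against the one-sided alternative hypothesis" of 0.75 or more. Section 9.5 gives the level and power: "the study will have 80% power at the 5% significance level for testing the null hypothesis". It asks for 40 patients with a 6-month visit out of 50 enrolled, and quotes 80.4% power at a realized level of 0.047.

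The result is to be summarized differently. Sections 9.2 and 9.4.1 both call for the observed proportion with "a two-sided exact 95% confidence interval (CI) per the Blyth-Still-Casella method". Neither section names a test statistic, a p-value rule or a responder count. Section 9.4.2 says only that the endpoint is binary.

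Straight after the interval, 9.2 gives two decision sentences. One declares success by reference to 75%. The other treats the therapy as not worth more study, unless it is developed further, "if the data are consistent with the conclusion that no more than 50% of treated patients can be expected to show a positive response". Section 9.1 says that no formal SAP will be produced before database lock.

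**The concern.** A one-sided 5% test corresponds to a one-sided 95% lower bound, which is the lower end of an equal-tailed 90% interval. A two-sided 95% interval is stricter at the lower end, roughly a one-sided 2.5% test. If both could be used to judge compatibility with a rate of 50% or less, some result may reject the null under one and fail to exclude 50% under the other.

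The wording invites this. The rule asks what the data are consistent with, which is the usual language of a confidence interval, and it follows the only interval the plan names. The stated null and alpha point to the test instead. At stake is whether a borderline result is reported as a rejected null or as grounds not to continue without further development, in an open-label, single-arm study with no later document planned to settle the matter.

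**Working it through.** **Inputs.** Null rate 0.50, one-sided (9.2); design alternative 0.75 (9.2, 9.5); significance level 5% and target power 80% (9.5); 40 evaluable and 50 enrolled (9.5); two-sided exact 95% Blyth-Still-Casella interval (9.2, 9.4.1). X is the number of responders, binomial(n, PT).

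**The plan's own figures.** The enrolment target reproduces: 40/(1 − 0.20) = 50. The quoted 80.4% power and 0.047 level do not reproduce at n = 40. They match n = 23 with a cut-off of 16 (alpha 0.0466, power 80.37%). That match is with a one-sided 5% exact test, so it supports reading the 5% in 9.5 as one-sided.

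**Test at n = 40.**
- P(X ≥ 25 | 0.50) = 0.0769: not rejected.
- P(X ≥ 26 | 0.50) = 0.0403: rejected.
- P(X ≥ 27 | 0.50) = 0.0192: rejected.

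The cut-off is 26/40 (65%).

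**Interval at n = 40.** Write P(X = 26 | 0.50) = 0.0403 − 0.0192 = 0.0211. At a rate of 0.50, counts 14 to 26 have total probability 0.9615. The method treats responders and non-responders symmetrically, so dropping 26 also drops 14 and leaves 0.9615 − 2 × 0.0211 = 0.9193, below 0.95. The interval for 26/40 must therefore contain 0.50. Computed limits:
- 26/40: about 0.48 to 0.79 (Clopper-Pearson 0.483 to 0.794).
- 27/40: about 0.51 to 0.81 (Clopper-Pearson 0.509 to 0.814), which excludes 0.50.

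By contrast, the equal-tailed 90% Clopper-Pearson interval at 26/40 is 0.508 to 0.775. Its lower end is the bound that corresponds to the one-sided 5% test, and it excludes 0.50.

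**How often it matters.** The procedures disagree only at X = 26, so its probability is P(X ≥ 26) − P(X ≥ 27):

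| True rate | P(X ≥ 26) | P(X ≥ 27) | P(X = 26) |
|---|---|---|---|
| 0.50 | 0.0403 | 0.0192 | 0.021 |
| 0.65 | 0.5721 | 0.4408 | 0.131 |
| 0.70 | 0.8074 | 0.7032 | 0.104 |
| 0.75 | 0.9456 | 0.8968 | 0.049 |

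The first and last rows also give the operating characteristics: alpha 4.0% and power 94.6% if the test governs, 1.9% and 89.7% if the interval does.

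**Other evaluable numbers.** Smallest count that rejects a rate of 50% or less:

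| n | 40 | 41 | 42 | 43 | 44 | 45 | 46 | 47 | 48 | 49 | 50 |
|---|---|---|---|---|---|---|---|---|---|---|---|
| One-sided 5% | 26 | 27 | 27 | 28 | 28 | 29 | 30 | 30 | 31 | 31 | 32 |
| One-sided 2.5% | 27 | 28 | 28 | 29 | 29 | 30 | 31 | 31 | 32 | 32 | 33 |

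The gap is one responder at every n.

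**The case against.** A reader might infer that the plan contradicts itself outright: that at 26/40 it rejects the null and, by its own interval, also calls the treatment unworthy of further study. The text does not support that. Sections 9.2 and 9.4.1 say the interval summarizes the response rate, and neither decision sentence refers to it. The 50% rule closely mirrors the null hypothesis, and 9.2 says the study is designed to test that null. It is reasonable to read failure to reject as the trigger and the interval as descriptive. On that reading 26/40 rejects, the rule is not met, and there is no conflict. Pairing a one-sided test with a two-sided descriptive interval is also common and not an error in itself. Finally, the rule carries a qualifier: it concerns further study without further development, not outright abandonment.

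All of this stands, and so does the narrow reach: one count out of 41 possible, with both procedures below 5% type I error and above 80% power. What remains is that the plan never says which reading applies. The interval is the only primary inference named in the methods, and the rule uses interval language directly after it.

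**Conclusion.** The point holds as a gap in specification. Two procedures are stated, neither is named as deciding the 50% rule, and at n = 40 they part at exactly 26 responders. That result is unlikely at the null or the design alternative, and has a probability of 10% to 13% for true rates of 0.65 to 0.70. The issue is minor.

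Confidence is high on the arithmetic, which rests on independent binomial responses, 40 evaluable patients and an exact interval symmetric in responders and non-responders. Confidence is only moderate that anyone would use the interval to apply the rule.

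Two neighbouring matters are not settled here. The interval at 26/40 also contains 75%, so aligning the 50% boundary does not define the success rule, under which "The treatment will be declared a success if the data support the conclusion that at least 75% of treated patients can be expected" to respond. And the power and level in 9.5 do not describe n = 40 under either procedure.

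**What to change.** In 9.2, state that the one-sided 5% exact binomial test governs the 50% decision, with rejection at 26/40 or more. Equivalently, the one-sided 95% lower Clopper-Pearson bound must exceed 0.50. State that the two-sided 95% interval is descriptive only. Give the cut-off for each evaluable n from 40 to 50, using the one-sided 5% row of the table above. In 9.5, replace the quoted power and realized level with those of the chosen rule at n = 40: 94.6% and 4.0%.

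Testing at one-sided 2.5% would instead bring the test into line with the planned interval, with a cut-off of 27/40 and 89.7% power at 0.75. That is acceptable but is a design preference, and it raises the bar by one responder.

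Either way the cost is a few sentences in 9.2 and 9.5, with no extra patients or data. The change should be made before any 6-month results are examined, including the preliminary analysis after 10 patients.

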9.3 Analysis Datasets

Participants who received study device and complete at least one follow-up visit (3-month visit) will be included in the study analysis.

Preliminary analysis will be performed after 25% (10 subjects) of study sample size complete the 6-month follow-up visit.

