4.4 Strategies for Recruitment and Retention

Participants will be recruited at the study investigator or sub-investigator clinical practices, via brochures / social media, and through an EPIC search.

Study Investigator Or Sub-Investigator Clinical Practices

A study investigator or sub-investigator will assess the medical record of potential subjects for eligibility and provide eligible participants with information regarding the study during the initial study visit and, if patients are interested, obtain informed consent.

IRB-approved study coordinator or co-investigator will guide interested people through written informed consent. Recruitment is expected to occur over four years. To achieve the primary objective, data from 40 patients will be required (i.e. completed GAE and at least 6 month visit) and the study would accrue 50 patients to account for an attrition rate of 20%.

Only NYULH individuals who are listed on the IRB-approved protocol will approach patients for consent.

Brochures / Social Media

A study brochure [attachment 3] will also be available in NYULH rheumatology, orthopedics, family medicine, and interventional radiology clinics and will be also disseminated on social media (e.g. Facebook, Twitter, blogging) to advertise for the study after IRB approval. The study brochure will include contact information for interested subjects to contact the study coordinator and/or PI.

DataCore/Epic Information for Recruitment

Potential study subjects will often be identified by the orthopedic sub-investigator. This study will utilize EPIC to identify subjects. IRB-approved study personnel will submit a request to NYULH DataCore via iLab after obtaining IRB approval to generate a report. The report will be requested to generate a list of potential subjects with a diagnosis of knee pain post TKA and who meet eligibility criteria from the electronic medical system of NYULH.

The research coordinator(s), PI, and co-investigators will have access to EPIC search results / DataCore report throughout the study active enrollment period. The report request will be submitted twice a month during the course of the study. The list will be filtered to identify patients who meet eligibility criteria listed in this protocol.

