4.6 Total Number of Participants and Sites

Data from 40 participant will be required and the study would accrue 50 patients to account for an attrition rate of 20%. Withdrawn subjects and subjects who did not completed at least the 6-month visit can be replaced.

The study will be conducted only at NYULH Hospitals. No subjects will be enrolled at external national or international sites.

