4.7.2 Handling of Participant Withdrawals or Termination

If a patient withdraws prematurely from the study due to the above criteria or any other reason, study staff should make every effort to complete the full panel of assessments scheduled for the follow-up visits. The reason for patient withdrawal must be documented. In the case of loss of follow-up, attempts to contact the patient will be made and documented in the patient's medical records. Every effort will be made to undertake protocol-specified safety follow-up procedures to capture AEs, serious adverse events (SAEs), and unanticipated problems (UPs). Withdrawn patients can be replaced (do not count toward the protocol-defined sample size).

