9.4.2 Analysis of the Primary Efficacy Endpoint(s)

The primary endpoint is the clinical success rate at 6-month follow-up compared to baseline as a binary assessment.

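### The single analysis set in 9.3 drops early-lost and never-embolized patients from the safety and technical-success rates, and the 6-month success rate has no stated denominator or missing-outcome rule

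*Combined protocol and SAP*

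**What the plan says.** - **Analysis set.** Section 9.3 is the only place that defines one: "Participants who received study device and complete at least one follow-up visit (3-month visit) will be included in the study analysis".
- **Primary outcome.** Section 9.4.2: "The primary endpoint is the clinical success rate at 6-month follow-up compared to baseline as a binary assessment". Section 9.2 declares success if the data support that "at least 75% of treated patients can be expected to show a positive response".
- **Sample size.** Section 9.5: "the study should have 40 patients who completed the 6 months visit". Sections 3.1 and 4.4 use the same count, and 50 are to be enrolled to allow for 20% attrition.
- **Replacement.** Section 4.6: "Withdrawn subjects and subjects who did not completed at least the 6-month visit can be replaced". Section 4.7.2 adds that withdrawn patients do not count toward the sample size.
- **Data after withdrawal.** Under 4.7.2, "study staff should make every effort to complete the full panel of assessments scheduled for the follow-up visits". Section 6.3.5 collects questionnaires at an early termination visit.
- **Safety and technical success.** Sections 9.4.3 and 9.4.4 define both rates as proportions of patients and name no set. Section 7.3 requires every AE on study to be documented, from consent onward. Section 2.2 makes embolization from at least one feeding artery part of technical success.
- **Later documents.** Section 9.1 says there will be no formal SAP before database lock.

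**The concern.** The trial has one arm and a fixed 50% null, so each reported rate depends directly on who is in its denominator. The one set that is defined fits none of the three main uses well.

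For safety, a treated patient who has an early AE and never attends month 3 is outside the set. For technical success, a patient whose catheterization fails has not received the device and is also outside it, although that is the kind of failure the endpoint should count. For the primary outcome, the set leaves out treated patients lost before month 3 and takes in patients who cannot be classified at month 6.

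The study is open label and has a preliminary analysis after 10 patients complete the 6-month visit. A denominator settled after that look could be influenced by the data.

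**Working it through.** **1. The plan's own figures.** 40/(1 − 0.20) = 50, so the enrolment figure reproduces. The 80.4% power and 0.047 level that 9.5 attaches to 40 patients do not: the exact one-sided 5% test of 50% at n = 40 needs at least 26 successes, with level 0.040 and power 94.6% at a true rate of 75%. That is a separate matter, and nothing below rests on it.

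**2. Where each kind of patient falls.**

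| Patient | Treated (9.2) | 9.3 set | Six-month completer (9.5) |
|---|---|---|---|
| Procedure fails before embolic | No device given | Out | Out |
| Treated, lost before month 3 | In | Out | Out |
| Treated, month 3 seen, month 6 missing | In | In, no outcome | Out |
| Treated, month 6 seen (month 3 also attended) | In | In | In |

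Nothing in 9.2 to 9.5 says how to score the third row, or whether data obtained under 4.7.2 or 6.3.5 enter the primary analysis. The replacement rules govern accrual; they do not say whether a replaced patient stays in the analysis.

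**3. Effect on the success rate.** Assumed: 50 treated, 3 lost before month 3, 7 lost between months 3 and 6, 30 observed successes. The p-value is the one-sided exact binomial P(X ≥ 30 | n, 0.5), with missing counted as non-success.

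| Denominator | Rate | p |
|---|---|---|
| Completers | 30/40 = 75% | 0.001 |
| 9.3 set | 30/47 = 64% | 0.039 |
| All treated | 30/50 = 60% | 0.10 |

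With missing counted as success, the last two become 37/47 = 79% and 40/50 = 80%. In a milder case, with 45 treated and 5 lost after genicular artery embolization (GAE), all treated gives 30/45 = 67% (p = 0.018).

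**4. Direction of bias.** With T treated, L lost, true rate p in all treated and rate r among the lost, the completer rate is (T·p − L·r)/(T − L). For T = 50, L = 10, p = 0.5:

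- r = 0: 25/40 = 0.625
- r = 0.25: 22.5/40 = 0.5625
- r = 0.5: 20/40 = 0.50
- r = 0.75: 17.5/40 = 0.4375

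The completer rate is too high if the lost do worse, right if they do the same, and too low if they do better.

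**5. Safety and technical success.** With 50 procedures started and one failing before embolic, technical success is 49/50 = 98%. Under 9.3 the failure is removed and the rate is 49/49 = 100%. An early-lost patient with an AE is likewise worth up to 1/50 = 2 percentage points of the AE rate.

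**6. Power if all treated, missing as non-success, were primary.** With 50 treated and 75% success among completers, the response rate is 0.75 × (50 − L)/50. The exact one-sided 5% test of 50% rejects at 32 or more.

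| L | Response rate | Power |
|---|---|---|
| 0 | 0.75 | 97% |
| 4 | 0.69 | 82% |
| 5 | 0.675 | 75% |
| 10 | 0.60 | 34% |

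**The case against.** The best defence is that the plan does lean one way on the primary outcome. Sections 3.1, 4.4, 4.6, 4.7.2 and 9.5 all point to six-month completers, treated patients in 9.2 can be read as the target of inference rather than a labelled set, and 9.3 may be meant as a wider set for the 3- to 24-month outcomes. This stands in part: a reader might infer three rival primary analysis sets, and the documents do not go that far. A completer denominator is implied. It is still never stated, and the only set that is stated differs from it.

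A reader might also infer that a completer analysis must inflate the success rate, with a false-positive chance of 17% to 44% when 10 of 50 are lost. The documents do not support that. The range assumes a cut-off of 26/40, which the plan does not give, and that at most a quarter of the lost would have succeeded. If three quarters would have succeeded, the chance is about 0.6%. If success means observing 30/40, it is 0.1% with non-informative loss and 6.8% if all 10 lost are failures. It also places all attrition after GAE, whereas the 20% applies to enrolled patients and can include loss between consent and procedure.

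On safety, 9.3 does not say that it governs AE rates, and AEs are captured from consent. The exclusion therefore follows from 9.3 being the only set named. It is not an expressed intention to leave out early events.

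Finally, counting missing as non-success is one convention, with a large power cost. A stated completer analysis with a sensitivity analysis would also close the primary-outcome gap.

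**Conclusion.** The point holds in this form. As written, 9.3 removes early-lost patients from the AE rate and pre-embolic failures from technical success. It also leaves the primary denominator and the handling of a missing 6-month outcome open. No SAP is planned before database lock to settle either.

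The possible size is material. In the upper-end case the same 30 successes give anything from 60% to 80% in all treated, depending on how the missing are scored, against 75% in completers. With 5 lost after treatment, the result still excludes 50% when missing is counted as non-success. These figures rest on assumed loss counts and an assumed number of successes. The documents give no basis for saying which way lost patients would differ, so no direction of bias is claimed. This should be fixed.

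**What to change.** 1. **9.3 and 9.4.4:** base procedure-related AE rates on every patient in whom the procedure was started (arterial access attempted), with no visit requirement. List AEs from consent onward separately for patients who never reach the procedure.
2. **9.3 and 9.4.3:** use the same procedure-started set for technical success, so that failed access and failure before embolic count as failures.
3. **9.3 and 9.5:** before the 10-patient preliminary analysis, state the primary denominator. Report success in six-month completers and in all patients who received embolic, and name which is primary. Use 6-month data obtained after withdrawal. Give the all-treated rate with missing scored as non-success and as success, to show the range.
4. **4.6 and 4.7.2:** state that a treated patient replaced for accrual stays in the safety set and in the all-treated analysis.

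The cost is wording; no new visits or data are needed, and 40 completers can remain the accrual target. The reported AE rate may be higher and the success rate lower. If all treated with missing as non-success is made primary, 9.5 should disclose the power loss shown in step 6.

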2.2 Secondary Objectives

The secondary objectives of the study are to determine

1. Safety of GAE evaluated by cumulative rates of adverse events (AE), as well as type, causality, and severity of each AE.
2. Feasibility / technical success defined as successful selective catheterization of target genicular artery(ies) and embolization from at least one feeding artery of the knee joint (with the embolization endpoint defined as suppression or reduction in the filling of (blood flow in) abnormal vessels visible on angiography (pruning of the distal abnormal vasculature, with patent genicular artery)).
3. Whether GAE is effective in improving:
 - a. Knee pain using the visual analog scale (VAS) at 3-, 6-, 12-, and 24-month post GAE
 - b. Knee symptoms using KOOS scores at 3-, 6-, 12-, and 24-month post GAE [60]
 - c. Self-reported quality of life using EQ-5D-5L scale at 3-, 6-, 12-, and 24-month post GAE [61].
 - d. Synovitis on MRA at 6- and 24- months post intervention
4. Effect of GAE on disease-specific biomarkers levels

3 Study Design and Endpoints

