3.2.2 Secondary Study Endpoints

Secondary efficacy endpoints are:

1. KOOS scores at 3-, 6-, 12-, and 24-month post GAE
2. VAS pain at 3-, 6-, 12-, and 24-month post GAE
3. Self-reported quality of life using EQ-5D-5L scale at 3-, 6-, 12-, and 24-month post GAE
4. MRA findings at 6- and 24-month post GAE
5. Pain medication usage at 3-, 6-, 12-, and 24-month post GAE
6. Feasibility / technical success
7. Knee-specific biomarkers at 3-, 6-, 12-, and 24-month post GAE
8. Number/rate, severity, and description of complications, adverse events, or poor outcomes that are secondary to the procedure, which will be summarized using counts and simple statistics (i.e., mean number of patients with complications.)

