5.2 Study Procedural Intervention(s) Description

On the day of the procedure (visit 3, day 0), the subjects will be given the choice of receiving intravenous anxiolytic and analgesic medication (moderate sedation) during procedure or proceeding with local anesthetic only. Arterial access site will be prepped and draped using sterile technique. Femoral artery access will be obtained with a micropuncture needle set and a vascular sheath or a guiding catheter will be placed in the femoral artery to maintain vascular access. A guiding catheter will be placed and lower extremity digital subtraction angiography (DSA) will be performed to depict the genicular arteries in all patients. Angiography will be performed to identify abnormal knee neovasculation arising from one or more of geniculate arterial branches.

After localizing the abnormal neovessels (abnormal vessels appear as tumor blush-type enhancement in the arterial phase, often accompanied by early venous drainage /hypervascula synovial tissue in the region of the target knee joint), a microcatheter will be inserted coaxially through the guiding catheter and selectively placed in the targeted artery(ies). If there is uncertainty about the angiographic findings, pre-embolization simulation can be performed with contrasted cone beam computed tomography (CBCT). This will allow the operators to know exactly what tissues will be receiving the microspheres. The abnormal vessels will be embolized with **100 µm Embozene™ Microspheres** solution under direct fluoroscopic visualization to prevent reflux and non-target embolization. Multiple geniculate arteries may be embolized until neovascularity is no longer seen.

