9.4.3 Analysis of the Secondary Endpoint(s)

Analysis of secondary endpoints include: (1) changes in the mean KOOS and VAS pain scores, the mean (2) the technical success rate (defined as the proportion of patients for whom the procedure was successfully completed); (3) the adverse event rate (defined as the proportion of patients showing each type of adverse event or any adverse event); (4) reduction in the usage of pain medication and the need for physical therapy. A point estimate and 95% confidence interval will be provided for each secondary outcome at each time and for the change in each outcome from baseline to each post-treatment follow-up visit. Changes in the outcomes from baseline to follow-up will be tested using the paired-sample Wilcoxon signed rank test for the KOOS and VAS scores and the McNemar test for the other measures which will be assessed as binary outcomes (e.g., whether or not the patient reported usage of pain medication on a daily basis).

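### The denominator for technical success is not stated, and the only analysis set, read literally, drops attempted patients who never received microspheres, which biases the rate upward

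*Combined protocol and SAP*

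**What the plan says.** Technical success is a secondary objective (2.2) and a listed secondary endpoint (3.2.2, "Feasibility / technical success"). Section 3.1 describes the pilot as designed to evaluate safety and feasibility.

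- **Definition.** Section 2.2 requires "successful selective catheterization of target genicular artery(ies) and embolization from at least one feeding artery of the knee joint". It adds an angiographic end-point: less or no flow in the abnormal vessels, with the genicular artery still open.
- **Analysis.** Section 9.4.3 lists "the technical success rate (defined as the proportion of patients for whom the procedure was successfully completed") and does not say which patients form the denominator.
- **Analysis set.** Section 9.3 has a single rule: "Participants who received study device and complete at least one follow-up visit (3-month visit) will be included in the study analysis". No enrolled, attempted-procedure or intention-to-treat set is defined, and section 9.1 says that no formal SAP will be prepared before database lock.
- **Order of the procedure.** In section 5.2 the device comes late. "After localizing the abnormal neovessels", "a microcatheter will be inserted coaxially through the guiding catheter and selectively placed in the targeted artery(ies"), and only then are microspheres injected. The section does not say how a patient with no abnormal vessel on angiography is classified.
- **Replacement.** Section 4.6: "Withdrawn subjects and subjects who did not completed at least the 6-month visit can be replaced". Section 4.7.2 adds that withdrawn patients who are replaced do not count toward the sample size.

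**The concern.** A feasibility rate should count the attempts that did not work. The clearest failure under 2.2 is a patient whose target artery could not be entered selectively or embolised. Because microspheres are given only after the microcatheter is in place, that patient receives no device and does not meet the 9.3 condition. The event that makes the patient a failure therefore also removes the patient from the only defined set, and the replacement rules do nothing to bring the patient back.

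The second 9.3 condition, a completed 3-month visit, has no bearing on a result that is known when the catheter is removed.

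At stake is a secondary feasibility result in replaced knees, where the plan offers no earlier technical success figure for this indication. A later trial or another centre could plan on a rate that omits the patients who could not be treated.

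**Working it through.** **Figure in the plan.** There is none to reproduce. The documents state no expected rate, target or sample size for technical success. Section 1.2.2 cites 100% technical success in a study of GAE for native-knee OA, and 100% in a study of embolisation for recurrent haemorrhage after hip or knee arthroplasty. Neither concerns pain after TKA.

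**Who is counted.**

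| Patient | Technical success under 2.2 | In the 9.3 set |
|---|---|---|
| Embolised, end-point reached, month 3 attended | Success | Yes |
| Some microspheres given, end-point missed, month 3 attended | Failure | Yes |
| Attempted, not catheterised or not embolised, no microspheres | Failure | No |
| Embolised, month 3 not attended | Success or failure, known on day 0 | No |
| Angiography done, no target vessel identified | Not settled by 2.2 | No |

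**Inputs.** N = 50 attempted procedures is an assumption, taken from the planned enrolment in section 9.5. Let f be the number attempted without any device given, and g the number given device who miss the end-point. Both are assumptions. Every patient given the device is taken to attend month 3.

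**Formulas.** Successes s = N - f - g. Rate over all attempts = s/N. Rate in the 9.3 set = s/(N - f). The ratio of the second to the first is N/(N - f), whatever g is. Intervals are exact (Clopper-Pearson) 95%.

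| f | g | All attempts | 9.3 set |
|---|---|---|---|
| 0 | 0 | 50/50 = 100% (92.9-100) | 50/50 = 100% (92.9-100) |
| 1 | 0 | 49/50 = 98.0% (89.4-99.9) | 49/49 = 100% (92.7-100) |
| 2 | 0 | 48/50 = 96.0% (86.3-99.5) | 48/48 = 100% (92.6-100) |
| 3 | 0 | 47/50 = 94.0% (83.5-98.7) | 47/47 = 100% (92.5-100) |
| 5 | 0 | 45/50 = 90.0% (78.2-96.7) | 45/45 = 100% (92.1-100) |
| 8 | 0 | 42/50 = 84.0% (70.9-92.8) | 42/42 = 100% (91.6-100) |
| 5 | 2 | 43/50 = 86.0% (73.3-94.2) | 43/45 = 95.6% (84.9-99.5) |

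Check on the last row: 50/45 = 1.111, and 86.0% × 1.111 = 95.6%.

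**The 3-month condition.** Its effect depends on who misses the visit. In the last row, if the two end-point misses do not attend month 3, the set gives 43/43 = 100%. If instead five of the successes do not attend, it gives 38/40 = 95.0%. The direction cannot be known in advance.

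**The case against.** The strongest reply is that no sentence applies 9.3 to technical success. The wording in 9.4.3 refers to patients in whom the procedure was completed, which most naturally implies that uncompleted procedures are in the denominator. The 3-month condition suggests that 9.3 was written with follow-up outcomes in mind. This stands in part: the link is by default, and a reader who infers that the plan expressly restricts technical success to device recipients goes beyond the text. But 9.3 speaks of the study analysis without exception, no other set exists, and no SAP is planned to supply one.

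A reader might also infer that the rate is forced to 100%, or that the endpoint cannot be answered at all. The documents do not support that. Receiving microspheres is not success under 2.2, and a treated patient who misses the angiographic end-point stays in the set as a failure.

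A third objection concerns size. The only technical success figures cited are 100%, and 2.2 asks for embolisation from just one feeding artery, so no failures or very few are plausible. At f = 0 there is no bias, and at f = 1 it is 2 points. This is fair, and it is why the low end is tabulated. Those figures come from other populations, so larger values are not ruled out.

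Finally, one might count every patient without an identifiable target vessel as a technical failure. Section 2.2 defines success relative to a target artery and does not settle this. It could equally be treated as a matter of patient selection.

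**Conclusion.** The point holds as a bias in a secondary endpoint under the literal rule. The plan's one analysis set excludes attempted patients who received no device, and it adds a follow-up condition that a day-0 outcome does not need. The first exclusion raises the reported rate by the factor N/(N-f): with 50 attempts and all treated patients succeeding, by 0 points at f = 0, 2 at f = 1, 10 at f = 5 and 16 at f = 8. These sizes rest on assumed failure counts and on full month-3 attendance among treated patients.

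The primary conclusion is not affected by this point. The success and no-further-study rules in section 9.2 use the clinical response rate, and technical success carries no hypothesis or target. The change should still be made, because feasibility is one of the questions that the pilot sets itself.

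**What to change.** In 9.3 and 9.4.3, state that:

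- technical success uses the 2.2 definition and is reported with an exact 95% confidence interval over all participants in whom the GAE procedure was started (arterial access), with no follow-up requirement;
- participants later withdrawn or replaced stay in that denominator;
- the number with no identifiable target vessel is reported separately, and the rate is shown both with and without them;
- the device-received and 3-month conditions apply only to post-treatment follow-up outcomes such as KOOS and VAS.

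The cost is a few lines of text, with no extra patients, visits or procedures. Section 4.7.2 already requires the reason for each withdrawal to be documented, so failed attempts that end in withdrawal should be traceable. The downside is that the reported rate may be slightly lower.
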